Q8. What is your facility doing to increase vaccine confidence and uptake among staff?

[figure not shown]
**Sample Size, Power, and Analytic Plan (IR-1):** The proposed study is a cluster randomization trial (stratified; RC-5). The intervention will be given at the cluster level (nursing homes). Study objectives and primary outcomes will be considered at both the cluster and individual levels (RC-1). There are several reasons why a cluster randomization was preferred over a traditional randomized controlled trial. First, the cluster randomization was preferred because the target of the intervention is a collective (i.e., a nursing home) rather than a particular patient. Second, cluster randomization was preferred due to potential contamination. Third, cluster randomization is compelling for practical reasons, when patient-specific level protocols would be nearly impossible like in the nursing home care (RC-2). The potential confounders will be balanced out by the randomization design. We will compare the observed confounders between two study arms and adjust them in the analysis if they are not balanced by design. Further, we will measure potential confounders before the start of exposure and report data on potential confounders with study results (CI-1; CI-4). We will monitor data collection for the RE-AIM metrics (surveys and interviews), routinely checking and following up with study sites to recover missing data (MD-1). We will use multilevel models such as mixed effects models or marginal models based on generalized estimating equation (GEE) method to estimate the intervention effect". Both methods are valid if the outcome data are missing completely at random. For data missing at random (i.e., depends on observed data only), mixed models can still provide valid inference and the weighted GEE methods will be considered to account for this type of missing data. We will also conduct sensitivity analyses to examine the robustness of results to missing data. Multiple imputation methods will be used to address the missing data in the covariates (MD-2, MD-4). Further, we plan to record and report all reasons for dropout and missing data and account for patients. Specifically, we will record reasons for missing data and perform analysis based on intention-to-treat principle as described below (MD-3). We have 126 nursing homes (62 in ECHO and 64 in ECHO plus) continuing to the phase 2 of the study. According to the CMS weekly data as of April 2021, the average weekly COVID-19 infection rate was 0.1%, average number of residents in nursing homes (cluster size) was around 75-80 and the coefficient of variation of cluster size was at about 0.76. Assuming 1% infection rate in the ECHO arm over the 9 weeks when additional topic sessions are provided in the ECHO plus arm, our study will have 80% power to detect a significant intervention effect if the infection rate is reduced to below 0.3% in ECHO plus arm. This calculation was based on a two-sided statistical test of difference between Poisson rates at alpha=0.05 and intracluster correlation coefficient (ICC)  $\leq 0.01$ . Our power will be below 80% if ICC is 0.05 or higher even if the infection rate is nearly zero in the ECHO plus arm. We will test the effectiveness of ECHO plus group by performing both individual-level analyses (primary) and cluster-level analyses (secondary) following the intention-to-treat principle. To account for intracluster correlations within nursing homes, we will use multilevel models such as mixed effects models or marginal models based on generalized estimating equation (GEE) method to estimate the intervention effect. The outcomes after 6-months of intervention will be analyzed using generalized linear models, with an appropriate link function depending on outcome type. Intervention effect on infection risk will be estimated as odds ratio or incidence

PRINCIPAL INVESTIGATOR (LAST, FIRST, MIDDLE): [name]

rate ratio based on logistic, Poisson or negative binomial regressions. State and cohort variations will be examined and accounted for using fixed or random effects in the models. Characteristics of residents (e.g., age, gender, cognitive function/dementia) and nursing homes (e.g., size, quality, baseline infection rate) will be adjusted. We hypothesize that the ECHO plus effect is heterogeneous and expect stronger intervention effects in subgroups without cognitive dysfunction/dementia as well as those who are younger (HT-1). Subgroup analysis with regard to key participant factors will be performed similarly to examine potential heterogeneity of intervention effects, further tested by interaction analysis (HT-2). If data are sufficient, we plan to explore the heterogeneity of intervention effect on infection rate based on the key participant factors such as age group, gender, dementia, insurance status, and race/ethnicity (HT-3). Outcomes will be assessed after the intervention is initiated (CI-3). Using all measures at 4, 6, 12 and 18 months, we will perform longitudinal analysis to evaluate if the intervention effect changes over time using the same modeling approach but add additional variables for time and time by intervention interaction. Correlations of repeated measures for the same resident will be taken into account in model estimation. Subgroup analysis with regard to key participant factors will be performed similarly to examine potential heterogeneity of intervention effects, further tested by interaction analysis. For cluster-level analyses, the aggregated outcomes (infection, hospitalization) are rates or proportions between 0 and 1 instead of being binary or count variables, we will use Beta regression to model them with a logit link function so that the coefficient can be interpreted as log odds ratio. We will also perform longitudinal analysis for aggregated outcomes based on Beta regression. All statistical tests will be two-sided, with p-values<0.05 considered statistically significant.

**D. Engagement Approach (PC-1):** Our investigative team has extensive experience with engaged research and has ensured incorporation of stakeholder engagement on multiple levels in the proposed study's planning and design (see appendix). Our pilot COVID-19 ECHO has received overwhelmingly positive feedback: "Penn State Project ECHO is one of the best eLearning communities I've participated in. It's an excellent way to learn from each other, discuss challenges and best practices." We assembled a robust stakeholder Advisory Board (AB; see letters, biosketches), with both new and established(\*) team partners, including: nursing home patients and their families ([name], [name]), nursing home staff/administration (Guardian Eldercare, Pleasant Acres, Presbyterian Senior Living, Spruce Manor Rehabilitation, Windy Hill Village), state and federal policy makers (PA's DOH\*, DHS\*, DA), payers (Highmark\*, Horst Group, Optum Health\*) and state professional organizations (PA Healthcare Association\*, Leading Age PA, PA Association of Community Health Centers\*). These synergistic partnerships across all facets of nursing home care will ensure our research continually focuses on what matters to stakeholders. To further enhance engagement, we will partner with existing nursing home resident and family advisory councils to bring additional voices to the research ensuring patient-centeredness. We have engaged each of our 16 stakeholders in this proposal's development and their input has shaped the study design. Our AB has convened twice in virtual meetings in the two months of this award. We have used virtual stakeholder meetings for the past four years for our current PCORI award and have developed effective, engaging best practices. The goals for this meeting include: review study aims and objectives, collaboratively discuss stakeholder roles and establish engagement guidelines (PCORI engagement principles), seek intervention feedback on curriculum design, and outline dissemination mechanisms for early results. Subsequent AB meetings will occur every other month, allowing for continuous feedback through an iterative process. Targeted agendas distributed before meetings with specific requests for stakeholder input will bolster

Fig 1. Patient-Centered Micro Network

PRINCIPAL INVESTIGATOR (LAST, FIRST, MIDDLE): [name]

discussions. To facilitate rapid feedback between meetings, we will use electronic surveys through REDCap. Stakeholders will also be offered Just-In-Time trainings to maximize engagement by providing a foundational research knowledge-base. A critical strength of the proposed research is to serve as a state-level demonstration project, ultimately leveraging our AB's national connections for widespread dissemination.

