**Study Population and Setting (RQ-3; PC-2):** We recruited 136 nursing homes from national nursing home lists, focusing primarily in Pennsylvania (PA), but including other sites within the northeast and Midwest from states that are demographically and geographically similar, including Connecticut, New Jersey, New York, Wisconsin, New Hampshire, Illinois, Vermont, Indiana, Virginia, Maryland, and Ohio. (CI-2). Given the differences in nursing home types and how they impact effective programming, our project focused on skilled nursing facilities eligible for the AHRQ-funded ECHO program. Nursing homes were recruited through collaborations with our stakeholders, including multiple state agencies (Department of Health-DOH, Department of Human Services-DHS, Department of Aging-DA) and state nursing home organizations (PA Healthcare Association, Leading Age PA) through phone calls and emails. COVID-19 ECHO participants include two nursing home staff members as required by the AHRQ program, and we encouraged participation by infection control staff and other facility leadership (e.g., medical director, nursing, administrators). Participants in our pilot study (n=16) and those who may have participated in any COVID-19 focused Project ECHO series will be excluded. These 112 nursing homes have already been offered the opportunity to participate in either Penn State's pilot AHRQ-funded ECHO cohort or by our colleagues at Wellspan Health. We were confident in the willingness of nursing home staff to participate in weekly, 90-minute ECHO sessions (the last 30 minutes are optional) over the proposed study period, as we have already piloted this weekly program early in the pandemic, resulting in 80% of participants (27 of 34) attending every week over the 6-week timeframe. Further, we have partnered with multiple state and local nursing home stakeholders who have shared with us in our conversations the critical nature of this intervention and the eagerness for nursing homes to be engaged to access this information. Although many stakeholders mentioned this, the feedback was particularly strong from [name], Director of Quality Initiatives for the Pennsylvania Healthcare Association, whose organization engages 200 nursing homes and 400 members and has a national umbrella organization through which to reach nursing homes in additional states. We are confident that through our conversations with our 16 stakeholders who provided letters of support for our proposal, including nursing home staff and administrators, three state agencies, three state professional organizations, and healthcare systems, we have a finger on the pulse of participant willingness to engage. Willingness to engage in ECHO is also strengthened by our overwhelmingly positive response to our pilot series. Half of these participants reported never participating in an ECHO series previously yet rated the experience highly as more powerful than traditional learning. These responses highlight the belief in the intervention and will strengthen willingness to participate regularly.

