**Effectiveness:** The *primary outcome* is COVID-19 infection rate reduction in nursing homes. This de-identified patient data will be obtained using The Nursing Home COVID-19 Public File along with three *secondary outcomes*: flu-like illness, COVID-19 hospitalizations, and deaths. Secondary outcomes will be collected through the National COVID-19 Nursing Home data file that is publicly available (<https://data.cms.gov/stories/s/COVID-19-Nursing-Home-Data/bkwz-xpvg>). Specifically, the variables that will be assessed include: Residents Weekly and Total Admissions, Residents Weekly and Total COVID-19 Deaths, Number of Residents with New Influenza, and Number of Residents with Acute Respiratory Illness Symptoms Excluding COVID-19 and/or Influenza. This data is also available for staff. Nursing home resident QOL (*secondary outcome*; PC-3) will be measured using CMS' Minimum Data Set, including emotional, symptom and functional statuses, behavioral disturbances, social support, patient engagement, and shared decision making. CMS data will be linked to residents at participating nursing homes (IR-3). We will collect several measures to assess how much COVID-19 ECHO is utilized in nursing homes (see attached Excel spreadsheet). Our Aim 2 proposed using the RE-AIM framework to critically evaluate the utilization of interventions in both trial arms. To accomplish this, for example, we will record and categorize participation in each session (e.g., number of staff per nursing home site, role of participants in nursing homes, engagement in sessions). At the beginning of each ECHO session, we ask that all participants place their name, email address, and affiliation in the chat box. In addition, we can pull zoom reports to identify participants and the length of time they joined each session (to ensure full participation). We will also offer continuing education credits, which is a second opportunity to record engagement and assess quality dimensions that explain participation (e.g., satisfaction, acceptability). Surveys at the end of the cohort will also provide feedback as to the utilization of best practices taught throughout ECHO sessions. Lastly, as described in the interviews, we will have questions specifically identifying how engagement in ECHO changed practice. Equally important, all data collection is guided by the RE-AIM framework in order to provide a complete picture of how ECHO facilitates practice change and supports adoption of best practices. **Implementation outcomes:** We will measure Reach by assessing the characteristics of nursing homes and staff who participate in the study and those who do not. We will then compare these data to the overall characteristics of PA nursing homes to assess representativeness. We will evaluate Adoption by assessing the characteristics of early adopters

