### I. Risks to Human Subjects

a. *Involvement of Human Subjects:* The proposed study includes human subjects in its research but poses no more than minimal risk. We will recruit a total of 200 nursing homes to participate in the proposed randomized controlled trial. We anticipate enrolling at least one representative from each nursing home, which may include administration, director of nursing, or infection control staff to participate in ECHO sessions if the nursing home is randomized to the intervention group. We anticipate including de-identified data to assess our primary outcome (COVID-19 infection rate reduction) from the publicly available PA COVID-19 Nursing Home Reporting System. *Sources of Materials:* This study's primary outcome will rely on de-identified data from a publicly available source (The Nursing Home COVID-19 Public File), in aggregate, describing de-identified nursing home resident cases of COVID-19, hospitalizations and death. Additionally, we will obtain identifiable nursing home resident data through PSU's secure access to Medicare data through the Administrative Data Accelerator. Data analysis by investigators will occur through secure remote computing. Given our reliance on only secondary data for nursing home residents' outcomes, they will not be required to consent to participation. However, we will create and share messaging to make them aware of the study for dissemination at the nursing home level. The data will be used for research purposes only.

b. *Potential Risks:* The minimal risks to human subjects in the proposed project include loss of confidentiality.

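### The representativeness part of Reach is benchmarked against Pennsylvania homes overall, which is narrower than the 12-state frame of AHRQ-eligible skilled nursing facilities from which homes were recruited

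*Combined protocol and SAP*

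**What the plan says.** **Recruitment frame.** Study Population and Setting states: "We recruited 136 nursing homes from national nursing home lists, focusing primarily in Pennsylvania (PA), but including other sites within the northeast and Midwest". The other states are then listed: "Connecticut, New Jersey, New York, Wisconsin, New Hampshire, Illinois, Vermont, Indiana, Virginia, Maryland, and Ohio". The same paragraph restricts the project to skilled nursing facilities that qualify for the AHRQ programme.

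**Reach.** Under Outcomes, the Implementation outcomes text reads: "We will measure Reach by assessing the characteristics of nursing homes and staff who participate in the study and those who do not". The next sentence says that the team will "compare these data to the overall characteristics of PA nursing homes to assess representativeness". Table 4 defines Reach as the absolute number, the proportion and the representativeness of homes and staff agreeing to take part, and names no reference population.

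**Primary-outcome source (a separate point).** Section I, Risks to Human Subjects, first expects to take the "primary outcome (COVID-19 infection rate reduction) from the publicly available PA COVID-19 Nursing Home Reporting System". A little further on, the same section says: "This study's primary outcome will rely on de-identified data from a publicly available source (The Nursing Home COVID-19 Public File". The Effectiveness paragraph names that same public file, and Table 4 names the national nursing home file.

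**The concern.** Representativeness asks whether the homes that joined resemble the homes that could have joined. That calls for a reference population equal to the eligible homes in the recruitment area. Here the reference is Pennsylvania nursing homes overall, while the sample can include homes in 11 further states and only one class of facility. A gap between the two could mean that unusual homes volunteered. It could also mean only that homes in other states, or eligible skilled nursing facilities in general, differ from Pennsylvania homes as a whole. As written, the comparison cannot tell these apart.

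What is at stake is a descriptive statement about generalisability. It matters because the Dissemination and Implementation Potential section uses RE-AIM, and Reach within it, to judge how well the intervention would spread nationally. Table 4 also lists representativeness under Adoption, again with no reference population, so the same gap may carry over there.

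**Working it through.** The plan states no figure for this point, so there is none to reproduce. The check is a comparison of the texts, a count, and a short piece of algebra.

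1. **States.** Pennsylvania plus 11 named states: 1 + 11 = 12. The representativeness rule gives a benchmark for one of them. No other section supplies one for the remaining 11.

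2. **Facility type.** Frame: AHRQ-eligible skilled nursing facilities. Benchmark: Pennsylvania nursing homes overall. These differ even within Pennsylvania.

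3. **What the comparison measures.** Take any home characteristic. Let *w* be the share of participating homes outside Pennsylvania, *x* the mean among participants, *μ* the mean among eligible facilities, and *B* the mean among all Pennsylvania homes, which is the planned benchmark. Then

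   sample mean − *B* = (1 − *w*)(*x*_PA − *μ*_PA) + *w*(*x*_other − *μ*_other) + *w*(*μ*_other − *μ*_PA) + (*μ*_PA − *B*).

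   The first two terms are selection, which Reach is meant to describe. The third is state mix and the fourth is facility type. Neither of the last two is selection, and the planned comparison reports only the sum.

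4. **Can it be sized?** No. The plan does not give *w*, and it gives no home characteristics by state. Two assumptions put limits on *w* alone. If each of the 11 other states supplied at least one of the 136 homes, *w* is at least 11/136 = 8.1%. If the Pennsylvania focus means that more than half of the homes are there, *w* is at most 67/136 = 49.3%. So between about one twelfth and one half of any difference between Pennsylvania and the other states would enter the comparison as state mix. The difference itself is unknown and could be small.

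5. **Does the plan treat state as relevant elsewhere?** Yes. The analytic plan will examine state variation in the outcome models and account for it with fixed or random effects. The Reach comparison has no such provision.

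6. **Outcome source.** Of the four places that name a source for the primary outcome, one names a Pennsylvania system (the earlier sentence in Risks to Human Subjects). Three name the national file: the later sentence in that section, the Effectiveness paragraph, and Table 4. The same section still gives 200 homes to be recruited, against 136 in the Study Design Overview, Study Population and Setting, and the timeline milestone. The Pennsylvania wording therefore looks like text that was not updated.

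**The case against.** The strongest defence is that Pennsylvania is the main recruitment state, that the plan describes the other states as similar in demography and geography, and that the Engagement Approach presents the work as a state-level demonstration. On that view the benchmark is a reasonable stand-in. This stands in part: the benchmark is too narrow, not irrelevant. But the similarity is asserted, and a comparison against all 12 states is what would test it.

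It is also fair to say that the consequence is small. Reach is descriptive, and the hypotheses under Secondary Aim 2 concern adoption, implementation and maintenance. That stands.

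A reader might infer more than the documents support:

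- *That all of Reach is judged against Pennsylvania.* It is not. The number and proportion of homes come from recruitment logs, and the contrast of participants with non-participants carries no stated state restriction. Only the representativeness benchmark is affected.
- *That the Reach conclusion will be wrong.* It may be distorted, in an unknown direction. The count of 11 states out of 12 is a count of state names, not of homes, and does not measure the distortion.
- *That homes in 11 states have no source for the primary outcome, or that cases would be counted differently by state.* No section assigns different homes to different sources. The opening of Outcomes mentions federal and state agencies in general terms, but the detail that follows names the national file and CMS data for effectiveness.
- *That the source wording contributes to the representativeness problem.* The two are unrelated.

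**Conclusion.** The point holds as a minor one. The only stated benchmark for representativeness covers one of the 12 recruitment states and is not limited to the eligible facility type, so an observed difference may reflect state mix or facility type rather than selection. This rests on reading the representativeness sentence literally and on homes outside Pennsylvania actually being in the sample, as Study Population and Setting says. The size of the distortion cannot be computed from the documents. The randomised comparison of ECHO plus with ECHO is not affected.

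The Pennsylvania-named outcome source is an internal inconsistency in the human-subjects text that needs an edit. It does not show that outcome data would be missing for any state.

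**What to change.** In the Implementation outcomes text and in Table 4, define the reference population as eligible skilled nursing facilities in all 12 recruitment states. Present the comparison by state or standardised to the recruitment mix, show Pennsylvania separately as well, and report the number of participating homes per state. State whether the same reference applies to representativeness under Adoption.

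Separately, in Risks to Human Subjects, remove the reference to data "from the publicly available PA COVID-19 Nursing Home Reporting System" and name the national CMS file as the primary-outcome source for all homes.

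The cost is a little more descriptive analysis, for which the national lists already used in recruitment are a starting point, plus a few sentences of editing. Randomisation, sample size and the outcome analysis do not change.

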#### **Secondary Aims:**

1. To compare the effectiveness of ECHO versus ECHO plus on other patient-centered outcomes, including quality of life (QOL), flu-like symptoms, hospitalizations, and deaths. *We hypothesize that nursing home participation in the COVID-19 ECHO will significantly improve QOL and decrease hospitalizations and deaths.*
2. To evaluate the impact of the COVID-19 ECHO on key implementation outcomes in nursing home settings using the RE-AIM framework. *We hypothesize that nursing homes in both intervention conditions will report similar levels of adoption, implementation, and maintenance at the end of phase 1. We also hypothesize that, after completion of phase 2, nursing homes receiving the ECHO plus intervention will have higher levels of adoption, implementation, and maintenance of COVID-19 infection control guidelines than nursing homes in the ECHO arm.*

If effective, the COVID-19 ECHO, combined with the national ECHO infrastructure, will provide a real-world solution for stakeholders to address infection control guideline implementation in nursing homes.

PRINCIPAL INVESTIGATOR (LAST, FIRST, MIDDLE): [name]

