
PRINCIPAL INVESTIGATOR (LAST, FIRST, MIDDLE): [name]

as well as barriers and facilitators (i.e., inner and outer contexts, Organizational Readiness for Implementing Change scale [ORIC], Practice Adaptive Reserve scale [PAR], Change Process Capacity Questionnaire [CPCQ]).

Table 4. Proposed Study Outcomes

Study Outcomes	Description	Data Source (Timing of Assessment)
Reach	Absolute number, proportion, and representativeness of nursing homes and staff who agree to participate	Study recruitment logs and staff survey (baseline)
Effectiveness	Primary outcome: COVID-19 infection rate reduction; Secondary outcomes: flu-like illness, hospitalizations, deaths, QOL	National COVID-19 Nursing Home data file and CMS Minimum Data Set (baseline, 4, 6, 12, 18 months)
Adoption	Absolute number, proportion, and representativeness of nursing homes and staff who initiate and complete the ECHO series; and barriers and facilitators for adoption	Study participation logs; staff survey (baseline, 6 months) with validated measures including ORIC, PAR, and CPCQ; and key informant interviews (6 months post intervention)
Implementation	Nursing home staff knowledge and attitudes towards the various intervention functions and components, their level of implementation, and barriers and facilitators for implementation	Selected items from CDC's Preparedness Checklist; staff surveys (baseline, 6, 12 months) with validated measures; and key informant interview (6 months)
Maintenance	Extent to which implemented guidelines for emergency preparedness in an infectious disease outbreak become part of nursing home policies post-intervention	Key informant interview (12 months)

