Implementation will be assessed in nursing homes (enactment fidelity) using CDC's COVID-19 Preparedness Checklist for nursing homes as well as barriers and facilitators (i.e., Implementation Climate questionnaire, Key Driver Implementation scale). For Maintenance, we will assess policies nursing homes utilize to incorporate best-practice guidelines on addressing COVID-19, quality improvement, and infection control into routine practice. All staff survey data will be collected through REDCap, HIPAA compliant survey software. Our implementation evaluation will finalize with key informant interviews with a subsample of nursing home administrators/staff (n=40) following an explanatory-sequential design. With this design, our team will use interview discussions to further explain the effectiveness results of the RCT (infection rates, hospitalizations, and deaths) in the own words of the implementers, as well as strategies being implemented to support maintenance. These interviews will also help the study team understand additional contextual factors that were not present in the original submission (e.g., vaccine rollout in nursing home facilities). Main guiding questions (probing questions will be added as needed) are organized under 3 major themes corresponding to our RE-AIM evaluation plan and are listed below:

Theme 1) Factors associated with differential study outcomes

Q1. How did the infrastructure of your organization (size, networks, or physical layout) affect the study outcomes?

Q2. Did you have sufficient resources to implement and administer the strategies presented in ECHO sessions?

PRINCIPAL INVESTIGATOR (LAST, FIRST, MIDDLE): [name]

Q3. Do you consider that the participation of your nursing home facility in the study was a success or a burden? Why?

Theme 2) General implementation processes

Q4. How does the intervention compare to other alternatives that may have been considered or that you know about?

Q5. What is your perception of the quality of the ECHO sessions and supporting materials? Did they meet your expectations?

Q6. Tell me a new strategy that your facility implemented in the past 6 month as a result of participating in this study.

Theme 3) Experiences with Covid-19 vaccine rollout

Q7. Describe your facility's experience with the Covid-19 vaccine rollout. What are you doing to ensure that new residents get vaccinated?

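### Aim 2 predicts higher maintenance in ECHO plus, but the plan has no scored maintenance measure and no arm comparison, so the hypothesis cannot be tested as planned

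*Combined protocol and SAP*

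**What the plan says.** Secondary aim 2 makes two comparative statements about maintenance. At the end of phase 1 homes in the two arms "will report similar levels of adoption, implementation, and maintenance at the end of phase 1". Then, "after completion of phase 2, nursing homes receiving the ECHO plus intervention will have higher levels of adoption, implementation, and maintenance" than homes in the ECHO arm.

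Table 4 (Proposed Study Outcomes) defines Maintenance as "Extent to which implemented guidelines for emergency preparedness in an infectious disease outbreak become part of nursing home policies post-intervention". Its data-source cell holds a single entry, "Key informant interview (12 months". The neighbouring rows are richer. Adoption has participation logs, a "staff survey (baseline, 6 months) with validated measures including ORIC, PAR, and CPCQ" and interviews. Implementation has CDC checklist items, staff surveys at baseline, 6 and 12 months, and an interview.

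The paragraph after Table 4 says that policies bringing best practice into routine work will be assessed for Maintenance, without naming an instrument. It then describes "key informant interviews with a subsample of nursing home administrators/staff (n=40" in an explanatory-sequential design. The interviews are to help explain the trial results and to cover strategies that support maintenance. On the guide it says: "Main guiding questions (probing questions will be added as needed) are organized under 3 major themes". Eight questions, Q1 to Q8, follow.

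**The concern.** A prediction of a higher level in one arm needs a level in each arm, measured the same way in enough homes to compare. Maintenance is the only RE-AIM outcome with a between-arm prediction in aim 2 that has no log, checklist or survey behind it. Its one source is a qualitative interview with a subsample, meant to explain other results.

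If the plan is followed as written, a final statement that ECHO plus homes kept up the guidelines better (or did not) would rest on unscored accounts from a minority of homes, with no prespecified comparison. The reader of the final report could not tell a finding from an impression. The primary outcome and the CMS-based secondary outcomes are not affected.

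**Working it through.** **Step 1. What the hypothesis needs, against what is planned.**

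| Needed to compare levels of maintenance | What the documents provide |
|---|---|
| A measure matching the Table 4 definition (guidelines taken into facility policy) | Policies are to be assessed; no instrument or score is named |
| Data from both arms in known numbers | 40 interviews in total; no split by arm, no selection rule, no count of homes |
| Data at a stated time | Table 4 places interviews at 6 months (Adoption, Implementation) and 12 months (Maintenance); the total of 40 and the guide are given once and tied to neither wave |
| A question on the construct | None among Q1 to Q8 |
| A planned comparison | The Sample Size, Power, and Analytic Plan paragraph gives no coding, model or contrast for maintenance |

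**Step 2. The printed questions.** Q1 to Q3 cover infrastructure, resources, and whether taking part was a success or a burden. Q4 and Q5 cover alternatives and session quality. Q6 asks for a new strategy begun in the past 6 months. Q7 and Q8 cover vaccination. Q6 is the nearest, but it asks about uptake, not about retention or policy.

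**Step 3. The plan's own power figure.** The only one is 80% for infection rates of 1% vs 0.3%. Using a Wald test of two Poisson rates with design effect 1 + ((0.76² + 1) × 75 − 1) × 0.01 = 2.17, power is 81%, so that figure reproduces. It has no bearing on maintenance, for which no effect size or power is stated.

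**Step 4. Illustration of what 40 interviews could show.** Inputs from the plan: 40 interviews; 62 and 64 homes in phase 2; two-sided 0.05. Assumptions of mine: 20 vs 20, one person per home, each interview coded yes/no for guidelines being in policy, and 50% in ECHO.

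Share of homes reached, at most: 40 / 126 = 32%.

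Exact power is the sum, over all outcomes (a, b), of Bin(a; n₁, p₁) × Bin(b; n₂, p₂) wherever the two-sided Fisher p-value is below 0.05. At an assumed 70% response, 0.70 × 62 ≈ 43 and 0.70 × 64 ≈ 45.

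| Homes per arm | 50% vs 75% | Range for a 25-point gain, ECHO level 30% to 60% |
|---|---|---|
| 20 vs 20 | 27% | 23% to 32% |
| 62 vs 64 (full response) | 81% | 79% to 88% |
| 43 vs 45 (70% response) | 64% | 59% to 73% |

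With 20 vs 20, power is 41% for 50% vs 80% and 74% for 50% vs 90%.

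For a continuous score per home, the difference detectable with 80% power is (1.960 + 0.842) × √(2/n). That is 0.89 SD at n = 20 per arm and 0.50 SD at n = 63 per arm.

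**Step 5. The phase 1 statement.** Table 4 schedules no maintenance measurement at 4 months, whereas the Outcomes paragraph says outcomes are assessed at baseline, 4, 6, 12 and 18 months. These two places need to be reconciled for Maintenance.

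**The case against.** The best reply is that maintenance is not ignored. The text commits to assessing policies, names maintenance strategies as an interview topic, and allows probes beyond the eight main questions. The printed guide may belong to the 6-month round, as the recall period in Q6 suggests, so a 12-month guide could differ. The plan also refers to an attached spreadsheet of utilization measures and to a formal protocol still to be written, neither of which is shown.

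Much of this stands. A reader might infer that the hypothesis can never be tested, or that the interviews will yield nothing on maintenance. The documents support neither. Maintenance content may well be collected, and a crude coded comparison is possible, with 74% power for 50% vs 90% under the assumptions above. A reader might also infer that the 40 are chosen non-randomly; the text is silent on selection.

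Nor is it a maintenance gap that ORIC, PAR and CPCQ stop at 6 months. The plan uses them for barriers and facilitators of adoption, and they do not measure whether guidelines became policy.

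What does not stand is the step from content to test. Unspecified probes give no score by arm. The spreadsheet is described as covering how much ECHO is used, and Table 4 still lists only the interview. If the interviews are meant to be purely qualitative, the prediction of higher levels should not be attached to them.

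**Conclusion.** The point holds in a limited form: as planned, there is no scored level of maintenance and no specified comparison between arms, so this part of aim 2 cannot be tested as written. That conclusion comes from the text alone and does not depend on the power figures.

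The size is illustrative. For 50% vs 75%, exact power is 27% with 20 interviews per arm, against 81% with all phase 2 homes and about 64% at 70% response. These figures rest on an even split, one respondent per home, a yes/no code and a 50% level in ECHO. If the 40 are shared between the two waves, the 12-month number is smaller and power lower. The all-home figures also assume that the staff survey goes to every phase 2 home, which is the natural reading because no subsample is stated for it. The change is worth making because it is cheap, but it concerns one of three constructs in one secondary aim.

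**What to change.** 1. Add scored items to the 12-month staff survey already planned for Implementation. For each selected checklist item, ask whether it is written into facility policy and whether it is still in use.
2. Score the share of items met per home and compare arms by intention to treat with the planned models. State in advance how several respondents from one home are combined. If the cluster-level Beta regression is used, also state how shares of exactly 0 or 1 are handled.
3. List this survey as the Maintenance source in Table 4, and keep the interviews as explanation.
4. Add one question on facility policy to the 12-month guide, and state how many interviews take place at each wave and in each arm.
5. If the survey cannot be changed, relabel the maintenance hypothesis as qualitative and exploratory.
6. The 12-month survey does not serve the phase 1 statement. Either schedule a measurement for it or take maintenance out of that statement.

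There is no need to repeat ORIC, PAR and CPCQ at 12 months for this purpose.

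Cost: a slightly longer survey, one interview question and short edits to Table 4 and the analytic plan. Policy status would be self-reported, and with incomplete response the comparison may still fall short of 80% power, so the result should be reported as an estimate with its confidence interval.
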